Accrual Objective	Kidney transplant recipients (n=5) will receive standard of care (SOC) therapy consisting of alemtuzumab and steroid induction with mycophenolic acid and tacrolimus maintenance immunosuppression, plus induction and treatment for 6 months with belimumab.

Study Design	
This is an open-label pilot-study to evaluate the safety and efficacy of belimumab plus standard of care in the prevention of de novo donor specific antibody in adult subjects after kidney transplantation.
 
We will enroll 5 adult, living donor kidney transplant recipients who are sensitized, evidenced by: Positive sum Donor Specific Antibody (DSA) <1000 MFI and/or Panel of Reactive Antibodies (PRA)>0%. The primary endpoint of this study is de novo DSA production. There are two main reasons for selecting this patient population for our proposed study. 1) Sensitized patients are known to have higher rates of de novo DSA production and 2) Patients with low levels of DSA (sum DSA<1000 MFI) will enable more fidelity in determining the DSA that is produced de novo.

Study Duration:	
Kidney transplant recipients will receive the standard of care (alemtuzumab and steroid induction with mycophenolic acid and tacrolimus maintenance immunosuppression), plus six months of therapy with belimumab. Belimumab 10 mg/kg will be administered IV for 6 months at the following intervals: Day of transplant (Day 0), and then at Weeks 2, 4, 8, 12, 16, and 20 post-transplant.
 
Subjects will be treated for 6 months with belimumab and followed for DSA production for 1 year post transplant.

Primary Study Objectives	
In this proposal we plan to determine (a) whether the addition of belimumab to the standard of care (SOC: alemtuzumab and steroid induction with mycophenolic acid and tacrolimus maintenance immunosuppression) is safe and effective in preventing de novo DSA production at 1, 3, 6, 9, and 12 months post-transplant.
 
Secondary efficacy endpoints will be 1) graft survival and function as determined by serum creatinine/eGFR and urine protein at 1, 3, 6, 9, and 12 months 2) rates of acute cellular and antibody mediated rejection, at 1, 3, 6, 9, and 12 months.

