Infusion reactions occurred more frequently on the first two infusion days and tended to decrease with subsequent infusions. Delay in the onset of acute hypersensitivity reactions has been observed and recurrence of clinically significant reactions after initial resolution of symptoms following appropriate treatment, have been observed. Therefore, patients should remain under clinical supervision for 3 hours after completion of the first 2 IV infusions. Should symptoms of acute hypersensitivity occur, an extended period of monitoring may be appropriate, based on clinical judgment. This may include, but is not limited to, monitoring vital signs and observing any untoward reactions. Beyond the first 2 IV infusions, subjects should be monitored during and for an appropriate period of time after administration according to the study sites' guidelines or standard operating procedure for IV infusions. Patients treated with belimumab should be made aware of the potential risk, the signs and symptoms of such reactions, and the importance of immediately seeking medical attention. Delayed-type, non-acute hypersensitivity reactions have also been observed and included symptoms such as rash, nausea, fatigue, myalgia, headache, and facial oedema.

For additional information on the risks associated with belimumab, refer to the package insert for Benlysta® (GlaxoSmithKlein) at:
https://www.gsksource.com/pharma/content/dam/GlaxoSmithKline/US/en/Prescribing_Information/Benlysta/pdf/BENLYSTA-PI-MG.PDF

In this study, belimumab will be administered in combination with standard of care immunosuppressants, which will include alemtuzumab, tacrolimus, mycophenolic acid and corticosteroids (standard taper) for all study subjects. There has been no experience with the use of alemtuzumab or tacrolimus in combination with belimumab, while there are data on the use of belimumab in combination with MMF and/or corticosteroids. As with all immunosuppressants, each of these agents has the potential to be associated with infections and/or malignancy.

Alemtuzumab: The most common adverse events associated with alemtuzumab are:

- Infusion reactions including moderate fever and chills
- Leukopenia

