3.5.1 Discontinuation of study treatment and premature patient withdrawal

Patients may voluntarily withdraw from the study treatment or from the study for any reason at any time. They may be considered withdrawn from the study if they state an intention to withdraw, fail to return for visits, or become lost to follow-up for any other reason. If premature withdrawal occurs for any reason, the investigator must make every effort to determine the primary reason for a patient's premature withdrawal from the study. The investigator should discontinue study treatment for a given patient or withdraw the patient from study if, on balance, he/she believes that continuation would be detrimental to the patient's well-being. Patients who discontinue study treatment should NOT be considered withdrawn from the study and should continue to be followed until the end of the study, unless consent is withdrawn. Patients who are prematurely withdrawn from the study will not be replaced by an equal number of newly enrolled patients.

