3.6 Criteria for Terminating the Study

The Principal Investigator will review safety and efficacy criteria on an ongoing basis. The study enrollment will be halted and data reviewed by the Data Safety Monitoring Committee and the University of Wisconsin Health Sciences Institutional Review Board for any of the following:

- 1) If greater than two patients are discontinued from study treatment due to elevated liver function tests as described in the protocol.
- 2) If greater than two patients develop hypogammaglobulinemia and infectious complications resulting in discontinuation of study treatment
- 3) Death of one or more patients.

After this review, the Investigator, Data Safety Monitoring Committee and the IRB will jointly make a final determination regarding continuation, modification, or termination of the study. The study can be terminated at any time for any reason by the Principle Investigator or GlaxoSmithKline, Inc. Should this be necessary, the patient should be seen as soon as possible. The investigator may be informed of additional procedures to be followed in order to ensure that adequate consideration is given to the protection of the patient's interests. The investigator will be responsible for informing the DMC, IRB and the FDA of the early termination of the trial.

See Section 7.3 for information on the ICTR Data Monitoring Committee (DMC) for this study.

4. Selection of Subjects

Potential subjects will be identified prior to kidney transplant based on the following inclusion and exclusion criteria.

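### The liver stopping rules contradict each other at ALT 5 to below 8xULN, so it is unclear who stops treatment and who counts toward halt criterion 1 in section 3.6

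*Combined protocol and SAP*

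**What the plan says.** Section 3.6 lists three events that halt enrollment and send the data to the monitoring committee and the IRB. Criterion 1 reads: "If greater than two patients are discontinued from study treatment due to elevated liver function tests as described in the protocol". Criterion 2 has the same count: "If greater than two patients develop hypogammaglobulinemia and infectious complications resulting in discontinuation of study treatment". Criterion 3 is a single death. The synopsis fixes the size of the trial ("We will enroll 5 adult, living donor kidney transplant recipients who are sensitized"), and section 3.5.1 keeps it there: "Patients who are prematurely withdrawn from the study will not be replaced by an equal number of newly enrolled patients".

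Section 5.1.2 says what a liver discontinuation is, in two places:

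- *Liver Chemistry Stopping Criteria.* Treatment stops if any one of six items is met. Item 2 is ALT at or above 5xULN, with no further condition. Item 6 is ALT from 5 to below 8xULN in a subject who cannot be monitored weekly for at least 2 weeks. The closing sentence allows continuation only from 3 to below 5xULN, with bilirubin below 2xULN, no hepatitis symptoms or rash, and weekly monitoring for 4 weeks.
- *Increased Monitoring Criteria with Continued Therapy.* Two groups may continue. One is the 3 to below 5xULN group. The other is subjects from 5 to below 8xULN with bilirubin below 2xULN, no symptoms attributed to liver injury or hypersensitivity, and weekly monitoring possible for 2 weeks.

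On reporting, section 5.1.2 sends any liver stopping event to GSK within 24 hours. It requires SAE reporting when the ALT rise comes with raised bilirubin or INR. Section 7.2.1 sends SAEs to the DMC, with times only for events that are serious, related and unexpected. Section 7.3 provides biannual DMC review of all adverse events, extra meetings at the request of the DMC or the PI, and submission of reportable events under guidelines that are not reproduced.

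**The concern.** Two passages of one section give opposite instructions for the same subject. One requires treatment to stop, with the follow-up of a stopping event. The other permits treatment to go on with weekly laboratory checks. Section 7 calls for hepatic tests before each treatment cycle and belimumab is given on the "Day of transplant (Day 0), and then at Weeks 2, 4, 8, 12, 16, and 20 post-transplant", so the conflict would arise when staff decide on the next infusion.

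The conflict then reaches the trial-level rule. Criterion 1 sets no liver threshold of its own; it counts discontinuations as the protocol describes them. If the description is ambiguous, so is the count. Section 7.3 names section 3.6 as the place where the predefined stopping points are set. Section 1.3 gives a reason for wanting them clear: "There has been no experience with the use of alemtuzumab or tacrolimus in combination with belimumab".

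A smaller question is who hears of a liver stop. An isolated ALT rise that stops treatment is not automatically an SAE, so the stated SAE route to the DMC may not apply.

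**Working it through.** There is no figure in the plan to reproduce. Section 9 is descriptive, and no rate or operating characteristic is given for the halt rule. The check is a comparison of texts, followed by a count.

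**Step 1. Apply both texts to each kind of subject.** Write A for ALT as a multiple of ULN.

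- A from 3 to below 5, bilirubin below 2xULN, no symptoms, weekly monitoring for 4 weeks possible: the stopping criteria and the continued-therapy criteria both allow continuation. They agree.
- A from 5 to below 8, bilirubin below 2xULN, no symptoms, weekly monitoring for 2 weeks possible: item 2 says stop and the continued-therapy criteria say the subject can continue. **They conflict.**
- A from 5 to below 8, monitoring not possible: item 2 says stop and item 6 says stop. They agree, but everyone who meets item 6 has A of at least 5 and so already meets item 2. Item 6 adds no one.
- A from 5 to below 8, with symptoms or with bilirubin at or above 2xULN: item 2 says stop and the continued-therapy criteria do not apply. No conflict.
- A of 8 or more: item 2 says stop and no text allows continuation. No conflict.

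**Step 2. See whether either reading leaves the text intact.**

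- If item 2 governs, the 5 to below 8xULN continuation group contains no one and item 6 is redundant. The continued-therapy instruction for ALT falling from 5 to below 8xULN into the 3 to below 5xULN range would also have no subject on treatment to apply to.
- If the continuation clause limits item 2, then item 2 as written is too broad, and the closing sentence of the stopping criteria, which ends continuation at 5xULN, is incomplete.

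Either way some text has to change. The documents do not settle which.

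**Step 3. Carry the ambiguity into criterion 1.** More than two of 5 means at least 3, and 3/5 = 60%. Let u be the number of subjects with an undisputed liver discontinuation and d the number in the conflicting group, with u + d no more than 5.

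- If item 2 governs, the count is u + d.
- If the continuation clause governs, the count is u, unless a subject later meets another item, such as item 4 on persistence.

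The two readings give different answers whenever u is at most 2 and u + d is at least 3:

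- u = 2, d = 1: 2 + 1 = 3, criterion met; or 2, not met.
- u = 0, d = 3: 0 + 3 = 3, criterion met; or 0, not met.

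One disputed subject is therefore enough to decide the matter. No event rate is assumed.

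**Step 4. Trace a non-serious stop to the DMC.** For an isolated ALT stop that is not an SAE, section 5.1.2 names GSK and not the DMC. The times in section 7.2.1 cover only serious, related and unexpected events. In section 7.3 the extra meetings are optional and the guidelines are not in the documents. What remains with certainty is the biannual meeting. Under criterion 2 the corresponding case is a severe but not serious infection with low IgG, which should be rare. With 5 subjects, no replacement and one discontinuation each, routing all such events would add at most 5 × 1 = 5 notices.

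**The case against.** The best defense of the liver text is a sentence in the continued-therapy part of section 5.1.2: a subject who at any time meets a stopping criterion is to be handled as a stopping event. Read as a rule of precedence, it lets item 2 win. That gives an outcome but does not reconcile the text, because it leaves a continuation group that no subject can enter and an item 6 with no function. Staff who read only the continuation paragraph would act differently from staff who read only item 2.

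It can also be said that the conflict would be noticed. The GSK medical monitor must hear within 24 hours on either path. Section 3.6 adds two further safeguards: "The Principal Investigator will review safety and efficacy criteria on an ongoing basis" and "The study can be terminated at any time for any reason by the Principle Investigator or GlaxoSmithKline, Inc". These points stand and limit the consequences. They do not tell anyone how to count under criterion 1.

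On DMC notification the objection is stronger. Section 7.3 commits to sending reportable events under the DMC's own guidelines, which may already cover a non-serious stop. The PI may request a meeting, and the investigator may class an event as serious on medical judgment. This is why that point is optional.

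A reader might infer more: that a count of 3 of 5 is too high for criteria 1 and 2 to act in time, or that slow DMC review would expose other subjects to avoidable infusions. The documents do not support either. They give no discontinuation rate and no accrual rate, so any such probability or exposure would be an assumption. The third event also triggers committee and IRB review whether or not enrollment is complete. A time to notify the DMC is not comparable with a time to DMC review, and neither measures harm averted.

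**Conclusion.** The contradiction is real and rests on no assumption. For ALT from 5 to below 8xULN with bilirubin below 2xULN, no symptoms and monitoring possible, section 5.1.2 both stops treatment and lets it continue, and item 6 is redundant if item 2 applies as written. Criterion 1 inherits the ambiguity, and a single subject in this group can decide whether it is met. How often this would happen cannot be derived from the documents. This should be corrected.

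The DMC point is secondary. No section gives a time for telling the DMC of a non-serious discontinuation of the kind criteria 1 and 2 count, mainly an isolated ALT stop, so the committee may first see it at a biannual meeting. It would be wrong to conclude that such events go unwatched: GSK is told of a liver stop within 24 hours, the PI reviews continuously, and the uncited content of the DMC guidelines may close the gap. Nothing here shows that the halt count itself is wrong.

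**What to change.** 1. In section 5.1.2, reconcile items 2 and 6 of the stopping criteria, and the closing sentence of that list, with the 5 to below 8xULN group in the continued-therapy criteria, so that each subject falls under one instruction. Which instruction applies is a clinical decision for the sponsor-investigator and GSK; no threshold or rule is proposed here.
2. In section 3.6, state which liver discontinuations criterion 1 counts, by reference to the reconciled items.
3. Optional: confirm that the DMC reporting guidelines cited in section 7.3 cover non-serious discontinuations of the kind criteria 1 and 2 count, and say so. If they do not, add these events to DMC notification with a stated time; the 14 business days already in section 7.2.1 could be reused.

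The cost of items 1 and 2 is amendment wording. Item 3 costs a cross-reference or, at most, 5 extra notices. The sample size, the visit schedule and the analysis do not change.

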1.3 Summary of Known and Potential Risks and Benefits to Human Subjects

Belimumab: Belimumab has been generally well tolerated in the Phase 2 and Phase 3 SLE studies. The majority of subjects in the SLE studies were receiving concomitant corticosteroids and/or other immunosuppressants including azathioprine and mycophenolate mofetil (MMF). Precautions will be taken to mitigate the risk of infections, infusion and hypersensitivity reactions, and the potential risk of malignancy. These precautions will include the use of the ICTR Data Monitoring Committee (DMC), which will review subject safety and efficacy data.

Common adverse reactions ($\geq 5\%$) in clinical trials were: nausea, diarrhea, pyrexia, nasopharyngitis, bronchitis, insomnia, pain in extremity, depression, migraine, and pharyngitis. Serious adverse reactions have included: infections, Progressive Multifocal Leukoencephalopathy (PML), Hypersensitivity reactions; including anaphylaxis, depression. .

PML

Progressive multifocal leukoencephalopathy (PML) resulting in neurological deficits, including fatal cases, has been reported in SLE patients receiving immunosuppressant pharmacotherapy, including belimumab. A diagnosis of PML should be considered in any subject presenting with new-onset or deteriorating neurological signs and symptoms. The subject should be referred to a neurologist or other appropriate specialist for evaluation. If PML is confirmed, study agent should be discontinued and consideration should be given to stopping immunosuppressant therapy.

If PML is suspected, this should be immediately reported to the Medical Monitor. The appropriateness of continuing study agent, while the case is being assessed, should be discussed.

Suicidality

Some autoimmune diseases have an increased risk of suicidal behavior and/or ideation [Bachen, 2009; Timonen, 2003; Stenager, 1992]. For this reason in studies of patients with autoimmune disease, patients should be clinically assessed for suicidal ideation and/or behavior at each visit, but not for study purposes. If patient exhibits suicidal ideations or it is verbally expressed, the PI will enter a note and refer the patient to a psychiatrist.

Dosing

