- **B Lymphocyte Analysis:** B-cell FACS panels will be used to measure changes over the course of therapy in the transitional, naïve, memory and plasma cell compartments. For the subsets of interest, absolute numbers of cells and proportions relative to all B cells for the individual subsets will be determined, as will activation status. Specifically we will address peripheral transitional, naive, memory and plasma cell populations prior to transplant and at 1, 3, 6, 9, and 12 months post-transplant. Further exploratory analyses will include the expression of BLyS receptors (BR3, TACI and BCMA) on B cells, frequency of alloreactive B cells (using tetramers) and an analysis of the effect of belimumab on IL-10 secreting B regulatory cells. Again these assessments will be performed prior to transplant and at 1, 3, 6, 9, and 12 months post transplant
- **T Lymphocyte Analysis:** Similar assessments will be made of T cell subsets prior to transplant and at 1, 3, 6, 9, and 12 months post-transplant. Specifically we will evaluate activated T cell and T regulatory cell populations.

- **Cytokine Analysis:** Quantification of serum BLyS and APRIL levels and cytokines/chemokines associated with T-helper skewing or activation will be performed prior to transplant and at 1, 3, 6, 9, and 12, months posttransplant
- **Immunoglobulin Analysis:** Quantification of total serum levels of Immunoglobulin levels (IgM, IgA, and IgG) will be performed prior to transplant and at 1, 3, 6, 9, and 12 months post-transplant.

7. Safety Assessments

The patient will be evaluated for safety, and adverse events will be documented according to the procedures of the investigational site. The investigator will determine the relationship of the events to the administration of belimumab.

Patients will be clinically assessed for suicidal ideation and/or behavior at each visit. If patient exhibits suicidal ideations or it is verbally expressed, the PI will enter a note and refer the patient to a psychiatrist.

Expected Adverse Events (AEs) \geq Grade 2, and all unexpected adverse events will be documented, graded, and assessed for causality to belimumab by the Principal Investigator.

All Serious Adverse Events (SAEs) will be reported to GlaxoSmithKline within 24 hours. SAEs that meet the FDA and IRB reporting criteria will be reported within the specified timeframe. Serious Adverse Events will be documented, graded, and assessed for causality to belimumab by the Sponsor-Investigator.

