Grade 3 Severe or medically significant but not immediately life-threatening; hospitalization or prolongation of hospitalization indicated; disabling; limiting self care ADL

Grade 4 Life-threatening consequences; urgent intervention indicated.

Grade 5 Death related to AE.

7.2 *Serious Adverse Events*

A Serious Adverse Event (SAE) is any untoward medical occurrence that at any dose:

- Is fatal
- Is life-threatening
- Requires or prolongs inpatient hospitalization
- Results in persistent or significant disability/incapacity
- Is a congenital anomaly/birth defect

The inpatient stay following the transplantation procedure will be considered SAE only if prolonged for more than 14 days.

A medical event that may not be immediately life-threatening or result in death or hospitalization but may jeopardize the subject or may require intervention to prevent a serious outcome, may also be considered serious (e.g. intensive treatment in an emergency room or at home for allergic bronchospasm; blood dyscrasias or convulsions that do not result in hospitalization; or development of drug dependency or drug abuse). Medical and scientific judgment must be exercised when classifying events as serious. The Investigator must determine both the intensity of the serious adverse event and the relationship of the event to the administration of study medications.

7.2.1 *Reporting*

It is the responsibility of the Investigator to promptly notify the Institutional Review Board of all unanticipated problems involving risk to human research subjects. All serious adverse events including fatal or life-threatening events experienced by study participants in the study will be reported to GlaxoSmithKline, Inc., to ICTR DMC, the FDA per applicable regulations, and the UW IRB according to current IRB guidelines.

Adverse Events that are:	Notify:
Serious Suspected/Related* Unexpected	GSK Medical Monitor: Within 24 hours DMC: Within 14 business days HSIRB: Within 14 business days FDA and all participating institutions as soon as possible, but no later than 15 calendar days after learning of the event
Life threatening or Fatal Suspected/Related* Unexpected	GSK Medical Monitor: Within 24 hours DMC: Within 24 hours HSIRB: Within 1 business day of learning of the event. FDA: Within 7 calendar days of learning of the event
*Events that are possibly, probably, or definitely related meet the criteria for "Suspected/Related"	

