7.3 **ICTR Data Monitoring Committee (DMC)**

We plan to utilize the UW ICTR Data Monitoring Committee (DMC) to oversee the study. The UW ICTR DMC is comprised of experienced members (core plus ad hoc) with expertise required to oversee this study. The DMC members will review protocol-specific reports created by statisticians using data pulled from the ICTR OnCore clinical research management system and Research Electronic Data Capture (REDCap) data management tool. These standard reports will include an overview of study objectives, a review of actual and projected accrual rates, an evaluation of patient demographics for balance of randomization, and a summary of the number and seriousness of adverse events. An interim analysis of study results may be performed and source documents may be reviewed to allow the DMC to independently judge whether the overall integrity and conduct of the protocol remain acceptable based on data provided and reported by the Principal Investigator. The DMC will make recommendations to the Principal Investigator that could include actions of continuation, modification, suspension, or termination.

In providing oversight for the conduct of this study, the ICTR DMC will meet biannually during the study to review all adverse events. Additional meetings may be scheduled as determined by the DMC or as requested by the PI. The predefined stopping points for this study are described in section 3.6 of this protocol. We will submit all reportable events to the DMC and the Health Sciences IRB in accordance with their reporting guidelines.

8. Ethical Considerations and Compliance in Good Clinical Practice

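### Section 3.6 obliges no enrolment halt for non-fatal serious infection with adequate IgG, nor for non-fatal graft loss, confirmed PML or life-threatening hypersensitivity

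*Combined protocol and SAP*

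**What the plan says.** Section 3.6 requires enrolment to be halted, and the data reviewed by the monitoring committee and the IRB, in three cases:

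1. More than two patients taken off study treatment for elevated liver tests.
2. "If greater than two patients develop hypogammaglobulinemia and infectious complications resulting in discontinuation of study treatment".
3. "Death of one or more patients".

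Section 7.3 adds no further trigger: "The predefined stopping points for this study are described in section 3.6 of this protocol".

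Other safety provisions act on the individual subject or on reporting:

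- **Drug stopping.** Section 1.3 stops the drug for confirmed PML. Section 5.1.2 stops it for a related Grade 4 event, and for IgG below 250 mg/dL with a severe or serious infection. Section 3.5 stops it on the investigator's judgement.
- **Graft failure.** Sections 5.1.3 and 7 provide for continued safety data collection.
- **Reporting to the funder.** Section 7: "All Serious Adverse Events (SAEs) will be reported to GlaxoSmithKline within 24 hours". Section 1.3: "If PML is suspected, this should be immediately reported to the Medical Monitor".
- **Reporting to the DMC.** Section 7.2.1 says that all serious adverse events go to the DMC. Its table sets a 24-hour DMC deadline for the row "Life threatening or Fatal Suspected/Related* Unexpected".
- **Meetings.** Section 7.3: "the ICTR DMC will meet biannually during the study to review all adverse events", and "Additional meetings may be scheduled as determined by the DMC or as requested by the PI".

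**The concern.** The study-level rule does not match the risks that the protocol itself names. Section 1.3 lists infections, PML and hypersensitivity including anaphylaxis as serious reactions to belimumab, and states that there is no experience of combining it with alemtuzumab or tacrolimus. Graft survival is a secondary endpoint. Yet among non-fatal harms, only liver discontinuations and infections accompanied by low IgG can oblige a halt, and each needs three subjects out of five.

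At stake is whether the next subject is exposed before anyone is obliged to review a first PML case, anaphylaxis or graft loss, or three infection discontinuations with adequate IgG. As written, a pause after any of these depends on someone choosing to act.

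**Working it through.** The plan gives no operating characteristics for section 3.6, so there is no figure to reproduce.

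**Step 1: each event against the three criteria.**

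| Non-fatal event | Criterion 1 (liver) | Criterion 2 (low IgG + infection + stop, at least 3 of 5) | Halt obliged? |
|---|---|---|---|
| Serious infection, adequate IgG | no | fails the IgG condition | no, even if all 5 are affected |
| Graft loss | no | no | no |
| Confirmed PML | no | not as such | no |
| Life-threatening hypersensitivity | no | no | no |

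PML is an infection, so three cases with low IgG and drug stopped would meet criterion 2. PML alone does not. A fatal event of any kind meets criterion 3. Section 3.6 gives no IgG cut-off for hypogammaglobulinemia; the 250 mg/dL in section 5.1.2 is a dosing rule.

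**Step 2: which subjects can be protected.** A halt stops enrolment, so it helps only if the trigger is met before the fifth subject enters. The relevant number is therefore the first four subjects. A three-subject trigger can protect at most 5 − 3 = 2, and a one-subject trigger at most 5 − 1 = 4.

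**Step 3: criterion 2 with and without the IgG condition.** Let p be the chance that a subject stops belimumab for serious infection, and f the share of such cases with low IgG (assumed 50%, independent between subjects). With n = 4:

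P(at least 3) = 4p³(1 − p) + p⁴ = 4p³ − 3p⁴

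For the present rule, p is replaced by pf.

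| p | Without IgG condition | Present rule, f = 50% | Gain |
|---|---|---|---|
| 5% | 0.0005 − 0.00002 = 0.05% | 0.006% | 0.04% |
| 10% | 0.0040 − 0.0003 = 0.4% | 0.05% | 0.3% |
| 20% | 0.0320 − 0.0048 = 2.7% | 0.4% | 2.4% |
| 32% | 0.1311 − 0.0315 = 10.0% | 1.4% | 8.5% |

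The 32% is the rate of any infection after alemtuzumab induction given in section 1.3. It is a high anchor, not a serious-infection rate. The other values of p, and f, are assumptions.

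**Step 4: a one-event criterion for PML, graft loss or life-threatening hypersensitivity.** With assumed per-subject rate p, P(at least 1 of 4) = 1 − (1 − p)⁴:

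- p = 1%: 1 − 0.9606 = 3.9%
- p = 2%: 1 − 0.9224 = 7.8%
- p = 5%: 1 − 0.8145 = 18.5%
- p = 10%: 1 − 0.6561 = 34.4%

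The figures in steps 3 and 4 are still upper bounds for a useful pause at each rate, because some events in the first four subjects may come after the fifth has enrolled. The documents do not give accrual timing.

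**The case against.** The strongest reply is that the discretionary cover is broad. Under section 3.6 the investigator reviews safety on an ongoing basis, and the investigator or the funder may terminate the study at any time for any reason. The funder learns of every SAE within 24 hours. The DMC receives SAEs, may meet ad hoc and may recommend suspension. Subject-level rules stop the drug for PML, for related Grade 4 events, and for low IgG with serious infection. In a five-subject open-label pilot, this may seem enough.

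Most of that stands, and it rules out several stronger readings that a reader might infer:

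- *Enrolment would simply run on to the next biannual DMC meeting.* That needs inaction by the investigator, the funder and the DMC together. It is the worst case, not the expected one.
- *Expected events never reach the DMC.* Section 7.2.1 sends all SAEs to the DMC. What is missing is a deadline for expected events. The 24-hour row is limited to unexpected ones, and the reactions already listed in section 1.3 may be classed as expected.
- *Only investigator judgement could stop the drug for graft failure.* The related Grade 4 rule in section 5.1.2 can apply too.
- *The benefit should be computed on all five subjects.* At p = 32% that would give 19.1% for the criterion without the IgG condition instead of 10.0%, but an event in the fifth subject can spare nobody.

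What the reply does not supply is an obligatory halt. The plan already accepts that some events should not be left to discretion, since it lists liver discontinuations and death.

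**Conclusion.** The gap in the text is certain: section 3.6 obliges no halt for these non-fatal events, and no other section supplies one. The practical benefit of closing it is small. For infection, the gain over the present rule is about 0.04% to 8.5% across p = 5% to 32% at f = 50%, with at most two subjects protected. For the other harms, the chance of a trigger among the first four subjects is 3.9% to 34.4% across p = 1% to 10%, with at most four protected. Either benefit may be zero, depending on accrual. These sizes rest on assumed event rates and independence between subjects; only the 32% comes from the protocol. The change is worth making because the harms are irreversible or life-threatening, the combination is untried, and the cost is low. The documents do not support a claim that subjects are unprotected.

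**What to change.** Amend section 3.6 as follows, keeping the existing halt-and-review so that continuation remains a possible outcome:

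- **Criterion 2.** More than two patients stop study treatment because of a severe or serious infection, whatever their IgG level. Keep the present low-IgG combination as an alternative, so that nothing counted today is lost.
- **New criterion 4.** One or more of: confirmed PML; graft loss not clearly unrelated to belimumab; life-threatening hypersensitivity or infusion reaction not clearly unrelated to belimumab.

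Subject-level dosing rules do not change.

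Two limits remain. One or two serious infections would still oblige no halt, because the count in criterion 2 is unchanged. The relatedness wording in criterion 4 leaves some room for judgement.

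The cost is protocol wording and an occasional short enrolment pause that may prove unnecessary. This includes pauses for Day 0 reactions that cannot be separated from alemtuzumab, which is given the same day and has infusion reactions among its most common adverse events (section 1.3).
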